**Punch Minigrafts versus Transverse Needling or Combination of
Both in Treatment of Non-Segmental Vitiligo**

INTRODUCTION

Vitiligo is a common pigmentary cutaneous disorder occurring with an incidence of 1-2% worldwide, without predilection for sex or race. ^(1, 2)

The disease is characterized by gradual loss of the normal color of the skin resulting from melanin pigment loss due to the underlying destruction of the melanocyte. ⁽³⁾

Vitiligo is a multifactorial disorder with many theories explaining its pathogenesis such as autoimmunity,⁽⁴⁾ self-destructing mechanisms,⁽⁵⁾ neural mediators,⁽⁶⁾ biochemicals,⁽⁷⁾ an imbalance of epidermal cytokines⁽⁸⁾ and genetic factors.⁽⁹⁾

Vitiligo is not a life-threatening disease, but it may cause a major social and emotional distress with significant impairment in the quality of life. ⁽¹⁰⁾

Clinically; vitiligo is classified into segmental, non-segmental and unclassified vitiligo .Non-segmental includes generalized, acrofacial,universal, mucosal (more than one mucosal site) , mixed (associated with segmental vitiligo) and other rare variants. Segmental vitiligo includes uni- ,bi- or pleuri-segmental subtypes. Unclassified includes focal or mucosal (one site) subtypes. ⁽¹¹⁾

Treatment options for vitiligo include attempting repigmentation of affected areas,

depigmentation of non-involving skin or camouflage if neither is effective. Repigmentation could be attempted using medical therapy, surgical modalities.⁽¹²⁾

Topical medications include corticosteroids or calcineurin inhibitors. Ultraviolet radiation therapy, such as narrow-band ultraviolet B light (NB-UVB), is also widely used. It is minimally invasive, has few adverse effects and provides a good response rate. Excimer laser or light has become available for use recently, and favorable

treatment results have been reported.⁽¹³⁾

When medical treatments are ineffective, surgical treatment is indicated.⁽¹⁴⁾

The basic principle of all surgical methods is transfer of melanocytes from uninvolved skin into a stable vitiliginous lesion not responding to other lines of

treatment, where they function as effective epidermal melanin units.⁽¹⁵⁾

Surgical modalites are divided into two groups, tissue grafting and cellular grafting.

Tissue grafting includes dermoepidermal grafts, split thickness skin grafts, punch

grafts/minigrafts, and epidermal grafts/blister roof grafts. While cellular grafting

includes cultured or non-cultured epidermal suspensions.⁽¹⁶⁾

Transverse needling is a recently described technique in the treatment of stable

vitiligo. It is believed to induce pigmentation in treated areas by physically moving

melanocytes from pigmented edges of the lesions into depigmented marginal areas

using a horizontal needle moving within the skin tangentially between the two zones.^(17, 18)

AIM OF THE WORK

The aim of this study is to evaluate the effectiveness and tolerability of autologous punch minigrafting, transverse needling technique or combination of both followed by narrow band ultraviolet B phototherapy (311 nm) in the treatment of patients with stable non-segmental vitiligo lesions.

PATIENTS

This study will be carried out on twenty patients having non segmental vitiligo recruited from the attendants of the dermatology and phototherapy outpatient clinics of the dermatology, venereology and andrology department, faculty of medicine, Alexandria University.

Approval of the medical ethics committee of Alexandria Faculty of Medicine will be obtained. An informed written consent for participation in the study and photography will be taken from every participant included in the study after full explanation of the study protocol.

❖ Inclusion criteria:

- Adult patients (>16 years old) of either gender having stable non segmental vitiligo, that is resistant to other lines of repigmentation therapy.
- Stability will be defined in terms of ;^(14,19,20)
 - Lack of progression of old lesions with the past 6 months.
 - No development of new lesions within the same period.
 - Absence of history of koebner phenomenon.
 - Absence of confetti lesions or hypopigmented lesions within the past 6 months.
 - Presence of repigmentation of depigmented areas by medications or spontaneously in the past 6 months.

- While resistance to therapy will be judged after receiving standard protocol of NB-UVB together with oral mini pulse dexamethasone at a dose of 2.5 mg on two consecutive weekly days for 3 months.⁽²¹⁾
- Patients having lesions showing absence (0%) or poor (<25% according to VASI score) repigmentation after this regimen will be considered resistant to medical repigmentation and indicated to surgery. ^(22,23)

Exclusion criteria:-

- Cases of active, progressive disease lacking criteria of stability previously mentioned.
- Patients with segmental or universal vitiligo covering more than 70% body surface area.
- Patients with known associated autoimmune diseases, bleeding tendency, current or history of skin neoplasia, photosensitive disorders or any contraindications to corticosteroids therapy.
- Patients with tendency towards hypertrophic scars or keloid formation.
- Pregnant female and lactating mothers.
- Patients with emotional and psychological instability.

METHODS

All included patients will be subjected to:

- History taking focusing on duration of the disease, age at onset , progression, site of lesions, number ,date and site of last activity of the affected lesions.
- Family history , previous medications and response to them and general medical history
- General clinical examination and determination of skin phototype.
- Dermatological examination for confirmation of the diagnosis.
- Base line VASI scoring.
- VETF scoring using wood's light examination.
- Base line standardized photography for the lesions.

For each included patient in the study, three main lines of surgical treatment will be used in different areas and compared to a non-surgically treated areas as control.

LINE 1; Autologous punch mini grafts:⁽²⁴⁾

Under local anesthesia, multiple 1mm holes will be made in the depigmented treatment area using 1mm punch graft instrument inserted to a depth of 2-4 mm to remove a small column of depigmented skin that is to be discarded. The punches will be situated at or very close to the border of the lesion to avoid leaving an achromic fissure and will be separated by 5-8 mm distance from each other.

On the donor area mostly is the gluteal area, punches will be harvested using the same sized punches very close to each other so that maximum number of grafts can be taken from a small area.

Then the harvested-punch minigrafts will be inserted into the recipient chambers, pressed firmly by saline soaked gauge for hemostasis and secured by sterile strips or a compression bandage if applicable.

LINE 2; Transverse needling technique: (17, 18)

Needling will be done for selected treatment patch using a 30 G disposable insulin syringe, going from the pigmented margins of the lesion into the vitiliginous patch, Position of the needle will be kept close to the dermoepidermal junction and movement will be from normal skin towards the lesion. Needle pricks may lead to oozing of a small drop of blood which will be managed by physical pressure. No dressings will be needed. The procedure will be repeated for selected lesions weekly for a duration of 3 months.

LINE 3;Punch minigrafts followed by transverse needling:

In a third lesion, punch minigrafts will be done as mentioned in line 1 and will be left to stabilize for 3 months then transverse needling will be done weekly for the margins of the lesion as well as the areas of the punch grafts toward the vitiliginous area.

- A fourth lesion will be chosen as a control lesion, to which no surgical treatment will be attempted.
- All lesions will receive NB-UVB therapy according to standard protocol twice weekly and the patients will continue on the oral mini pulse dexamethasone at 2.5 mg dose for two consecutive days weekly all through the study period.
- All included patients will be followed up for a duration of 6 months following interventions.⁽²⁵⁾
- Follow up will be done by clinical examination, wood's light and serial photography at each follow up visit.
- Clinical assessment of disease severity initially , after 3 months and at end of 6 months using **Vitiligo Area Scoring Index (VASI);**⁽²⁶⁾
For each body region, the VASI will be determined by the product of the area of vitiligo in hand units (which was set at 1% per unit) and the extent of depigmentation within each hand unit–measured patch (possible values of 0, 10%, 25%, 50%, 75%, 90%, or 100%).
The total body VASI will be calculated using the following formula by considering the contributions of all body regions (possible range, 0-100):

$$\text{VASI} = \sum_{\text{All Body Sites}} [\text{Hand Units}] \times [\text{Residual Depigmentation}]$$

- Serial photography will be done to evaluate type, pattern and extent of repigmentation.
- Assessments of repigmentation will be performed by two blinded dermatologists using a 5-point scale; grade 0 (no repigmentation), grade 1

(1%-5%), grade 2 (6%-25%), grade 3 (26%-50%), grade 4 (51%-75%) and grade 5 (76%-100%).⁽²⁷⁾

- Extent of peri punch repigmentation in mm using a ruler.
- Digital assessment of the size of the lesion and of the depigmented versus repigmented area using Adobe photoshop software.
- Patient satisfaction assessment using visual analogue scale (VAS) after treatment period grading as (VAS, 0-10; 0 grade will be defined as “Not satisfied at all” while grade 10 will be defined as “completely satisfied”).⁽²⁷⁾
- Time till appearance of repigmentation will be calculated for each procedure.
- Possible side effects of the NB-UVB (erythema , itching and burning) , of the systemic steroids (weight gain, increase in blood pressure, insomnia ,acne ,agitation or menstrual disturbances) or of surgery (ecchymosis , scaring , cobble stoning or color mismatching) will be reported.⁽²⁸⁾

ETHICS OF RESEARCH

Research on human or human products:

- ✓ Prospective study: Informed consent will be taken from patients. In case of incompetent patients, the informed consent will be taken from the guardians.
- Retrospective study: Confidentiality of records will be considered
- DNA / genomic material: Informed consent for DNA / genomic test and for research will be taken from patients. No further tests will be carried out except with further approval of committee and patients. If the samples will travel outside Egypt the researcher will be responsible for transportation and security approval.
- All drugs used in the research are approved by the Egyptian Ministry of Health

Research on animal:

- The animal species are appropriate for the test.
- After test, if the animal will suffer, it will be euthanized and properly disposed.
- After operation, it will have a proper postoperative care.

RESULTS

The results of the study will be tabulated and analyzed with the use of appropriate statistical methods and appropriate figures and diagrams in order to fulfill the aim of the work.

DISCUSSION

The results will be discussed in view of achievement of the aim, their significance and their comparison with previous related studies in literature.

REFERENCES

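### Nothing random, concealed or masked decides which of two identically grafted lesions becomes the combination lesion, so the combination versus graft-only contrast can be biased before needling begins

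*Protocol*

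**What the plan says.** The protocol compares treatments within patients. PATIENTS gives the number: "This study will be carried out on twenty patients having non segmental vitiligo". METHODS gives the structure: "three main lines of surgical treatment will be used in different areas and compared to a non-surgically treated areas as control".

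Line 3 repeats the Line 1 procedure in a separate lesion: "In a third lesion, punch minigrafts will be done as mentioned in line 1 and will be left to stabilize for 3 months". Only after that interval do the two lines part: "then transverse needling will be done weekly for the margins of the lesion as well as the areas of the punch grafts".

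On how lesions reach their lines, the protocol says little. LINE 2 reads "Needling will be done for selected treatment patch using a 30 G disposable insulin syringe", and the control is introduced with "A fourth lesion will be chosen as a control lesion, to which no surgical treatment will be attempted". It does not say who selects, by what rule, or when, and it mentions neither random assignment nor concealment.

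LINE 1 fixes the punch size and puts the punches at or near the lesion border. It leaves a range for spacing (5-8 mm) and depth (2-4 mm), and the grafts are "secured by sterile strips or a compression bandage if applicable". The only people described as blinded are the two dermatologists who grade repigmentation.

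**The concern.** Line 3 versus Line 1 is the one comparison that shows whether needling adds anything to grafting. Both lesions are grafted by the same method, so they ought to be exchangeable until needling starts. Two things can break that.

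- **Choice.** If a person decides which lesion is Line 3, a lesion expected to do well can be placed there.
- **Handling.** If the operator knows which lesion is Line 3 while grafting, the two can be grafted or dressed differently without breaching the protocol.

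Either can create a real difference in repigmentation that has nothing to do with needling. Blinded graders would record it faithfully, and it could be read as a needling effect. Allocation is a matter of trial conduct, so an analysis plan that is not shown cannot be relied on to repair it.

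**Working it through.** The protocol states no alpha, power, SD, effect size or sample-size calculation, so there is no figure to reproduce. The first two steps rest on the text; the last two are illustrations on stated assumptions.

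**1. When do Lines 1 and 3 differ?** LINE 3 adopts the LINE 1 method and adds needling after 3 months. From grafting to month 3 the planned treatment is the same. The label has no effect on planned treatment in that time, yet the text already refers to a distinct Line 3 lesion.

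**2. How much latitude does the operator have?** Spacing of 5-8 mm allows a ratio of 8/5 = 1.6 in graft density along a border. If grafts were laid out as a grid, the ratio per area would be 1.6² = 2.56. Depth may vary from 2 to 4 mm, and the dressing is conditional. Placement is largely specified, and the number of grafts is bounded by border length and spacing.

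**3. Illustration: a fixed bias.**
- From the protocol: n = 20 patients, one Line 1 and one Line 3 lesion each.
- Assumed: no true needling effect; two-sided 5% paired t-test; bias b of 5 or 10 percentage points of repigmented area, in the same direction in all patients; SD s of the within-patient difference 15, 20 or 25 points.
- Formula: noncentrality δ = (b/s)√20; critical value t(0.975; 19) = 2.093; false-positive rate = P(|T| > 2.093), where T is noncentral t with 19 degrees of freedom and noncentrality δ.

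| b | s | b/s | δ | False-positive rate |
|---|---|---|---|---|
| 0 | any | 0 | 0 | 5.0% |
| 5 | 15 | 0.333 | 1.491 | 29% |
| 5 | 20 | 0.250 | 1.118 | 19% |
| 5 | 25 | 0.200 | 0.894 | 14% |
| 10 | 15 | 0.667 | 2.981 | 81% |
| 10 | 20 | 0.500 | 2.236 | 56% |
| 10 | 25 | 0.400 | 1.789 | 40% |

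For scale, 20 pairs have 80% power for a true difference of about 0.66 SD.

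**4. Illustration: choice alone.** In 50,000 simulated trials per setting, the better-looking lesion goes to Line 3 with probability q, and that judgement correlates ρ with the true prognostic difference.

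| ρ | q = 0.5 (random) | q = 0.7 | q = 1 |
|---|---|---|---|
| 0.3 | 5.0% | 6.9% | 18.1% |
| 0.5 | 4.9% | 10.8% | 45.7% |

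A random draw restores the nominal 5% for the choice component, whether it is made before grafting or at month 3. The simulation does not model handling. A draw before grafting leaves the operator aware of the label while grafting; a concealed draw at month 3 closes both routes.

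**The case against.** **The timing of the label is inferred.** The words third and fourth may merely number the lesions. The protocol does not say who selects, who grafts, whether both lesions are grafted in one session, or when the Line 3 label is fixed. This stands. A reader might infer that the lesion is documented as singled out beforehand and that preference does enter the result. The text supports only that early labelling is the natural reading and that preference can enter.

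**Early labelling is not the root cause.** A reader might infer that labelling before grafting itself biases lesion choice. It does not: a random draw before grafting is fair as to choice, and a non-random choice at month 3, with the graft response visible, could be worse. The root gap is the absence of random, concealed allocation, and it touches all four lesions. This stands too. What early labelling adds is the handling route.

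**Operator discretion is limited.** Placement is specified, the number of grafts is bounded, and Line 3 is tied to the Line 1 method. All lesions receive the same phototherapy, the steroid is systemic, and no lesion-specific aftercare beyond the dressing is described. This narrows the handling route, but spacing, depth and dressing remain open.

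**An imbalance could be seen.** The protocol plans a 3-month assessment and serial photography, so a difference present before needling need not pass unnoticed. That is fair, and how such data are used may belong to the SAP. It does not prevent the imbalance, and a difference in graft quality may continue to act after month 3.

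**Attrition.** A reader might add that early drop-out distorts the comparison. A patient lost before month 3 loses both lesions together; this reduces n but favours neither line.

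**Conclusion.** The concern holds as a risk, not as a demonstrated bias. The protocol has two lesions treated alike for 3 months, no random or concealed rule for which becomes Line 3, and no masking of the operator. Preference in choosing or grafting that lesion can therefore bias the contrast on which the value of the combination rests, and blinded grading cannot undo it.

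The size is unknown. A reader might take the percentages in the working as the trial's actual false-positive rate; they are not. The bias, its constant direction, the SD and the paired t-test are all assumed, and only the 20 patients come from the protocol. The figures show that with 20 pairs a modest systematic preference would be enough to mislead.

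The change is worth making because it is cheap and removes both routes from this contrast. It is part of the wider absence of lesion randomisation and does not replace a remedy for that.

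**What to change.** Amend METHODS as follows.

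- In each patient, choose two comparable lesions and graft both by the LINE 1 method, in the same session, without labelling either as Line 1 or Line 3.
- After the month-3 photographs and before any needling, open a sealed, randomly prepared envelope that names which of the two receives needling (Line 3). The other remains Line 1.
- Compare Line 3 with Line 1 in patients who reach that draw.
- Allocate the remaining lesions to Line 2 and control at random at baseline, because the month-3 draw does not cover them. Contrasts between grafted and non-grafted lesions are protected only if the pair to be grafted is itself drawn at random from the eligible lesions.

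**Cost.** One envelope per patient at month 3, a baseline draw for the other lesions, and a few sentences of text. No extra patient or visit is needed. The price is that both lesions must be grafted together, which the protocol does not now require, and that the label must stay concealed until month 3.

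### No rule assigns the four lesions in each patient to punch grafting, needling, combination or control, so every between-lesion comparison is open to selection bias

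*Protocol*

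**What the plan says.** The METHODS section of the protocol sets up a within-patient comparison: "three main lines of surgical treatment will be used in different areas and compared to a non-surgically treated areas as control". The AIM OF THE WORK and the title also put the three techniques side by side, so both treatment-versus-control and between-technique contrasts are of interest.

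The wording on which lesion receives which condition is:

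- **Punch minigrafts (LINE 1):** the text refers only to the treatment area, as in "multiple 1mm holes will be made in the depigmented treatment area using 1mm punch graft instrument".
- **Transverse needling (LINE 2):** "Needling will be done for selected treatment patch using a 30 G disposable insulin syringe", and then "The procedure will be repeated for selected lesions weekly for a duration of 3 months".
- **Combination (LINE 3):** "In a third lesion, punch minigrafts will be done as mentioned in line 1".
- **Control (under LINE 3):** "A fourth lesion will be chosen as a control lesion, to which no surgical treatment will be attempted".

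The protocol does not say who selects, when, or by what criterion. It mentions no random sequence, no concealment, and no matching or stratification by body site or size. The word 'randomized' occurs only in the title of a cited study (reference 27). The protocol does not call itself randomised, so this is a missing rule and not a contradiction.

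**The concern.** Using each patient as their own control removes differences in age, phototype, disease history and systemic treatment. It does not remove differences between lesions of the same patient. The protocol itself treats lesions as differing: the history covers "site of lesions, number ,date and site of last activity of the affected lesions", and lesion size is measured digitally. None of this is tied to assignment.

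As written, whoever picks the lesions may know all of these features. They could, without any intent to mislead, give the more promising lesion to one technique and leave an unpromising one as control, or the reverse. The wording does not show that this will happen, but it permits it. All six pairs among the four conditions (4 × 3 / 2 = 6) depend on that choice. A difference in repigmentation could then reflect the lesion and not the technique.

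**Working it through.** The protocol gives no alpha, test, effect size, SD or power, so it has no figure to reproduce. The check has two parts.

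**1. Does any other provision close the gap?**

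- *Blinded grading by two dermatologists (METHODS):* acts at outcome assessment. It protects measurement, not the starting prognosis of the lesions.
- *Common NB-UVB and oral dexamethasone (METHODS):* equalise background treatment, not lesion characteristics.
- *Stability and resistance criteria (PATIENTS, inclusion criteria):* may narrow the range of prognosis. They are worded for patients having such lesions, do not expressly require all four study lesions to be resistant, and leave body site free.
- *Baseline records ("Base line standardized photography for the lesions", lesion site, digital size):* could reveal a measured imbalance, but not an unrecorded judgement by the person assigning.
- *A later analysis plan:* can adjust for what was measured. It cannot create an allocation after the lesions have been treated.

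None of these replaces an assignment rule.

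**2. How much could a systematic preference matter with 20 patients?** This part is an illustration.

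Inputs: n = 20 patients (protocol, PATIENTS). Assumed: a two-sided paired t-test at 0.05 and continuous normal differences. The shift b is the mean of the within-patient difference caused by lesion choice alone, in SDs of that difference. The documents do not give b, so a range is shown.

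Formula: the rejection probability is P(|T| > t₀.₉₇₅,₁₉), where T is noncentral t with 19 df and noncentrality d × √20, and the critical value is 2.093. For example, at d = 0.3 the noncentrality is 0.3 × 4.472 = 1.342.

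*No true effect (d = b):*

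| Shift b (SD) | False-positive rate |
|---|---|
| 0 (random assignment) | 5.0% |
| 0.1 | 7.1% |
| 0.2 | 13.6% |
| 0.3 | 24.7% |
| 0.5 | 56.5% |

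*True effect with the shift running against it.* Solving the same formula for 80% power at n = 20 gives d = 0.660. With d = 0.660 − b:

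| Shift b (SD) | Net difference (SD) | Power |
|---|---|---|
| 0 | 0.660 | 80% |
| 0.1 | 0.560 | 66.2% |
| 0.2 | 0.460 | 49.8% |
| 0.3 | 0.360 | 33.4% |
| 0.5 | 0.160 | 10.5% |

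The unrounded last value is 0.1047, so 10% to the whole percent.

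**Checks.** A Wilcoxon signed-rank test (20,000 simulations, continuous normal differences) at b = 0, 0.1, 0.2, 0.3 and 0.5 rejects in 4.6%, 7.2%, 12.9%, 23.9% and 54.8%, so the pattern does not depend on the t-test. When four lesions per patient are randomly permuted and prognosis correlates 0.2, 0.5 or 0.8 with outcome (40,000 simulations, paired t-test), the false-positive rate is 5.0%, 4.9% and 5.0%. Random assignment holds the error rate even when lesion prognosis matters strongly.

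**The case against.** The strongest reply is that this is an omission and not an error. The protocol never claims randomisation, concealment or matching, so no stated claim is broken. That is correct, but lesion assignment is a protocol element that must be fixed before treatment. A control that is simply to be chosen fixes it badly.

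Second, some of the wording is weak evidence. The LINE 1 phrase describes surgical technique, the repetition sentence in LINE 2 concerns lesions already picked, and the LINE 3 phrase merely counts. This stands. The point rests mainly on the selected needling patch, the chosen control and the absence of any rule elsewhere.

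Third, the resistance criteria narrow the spread of prognosis, and grading by percentage repigmentation partly allows for lesion size. Both soften the exposure without removing it, since body site and individual judgement remain free.

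Fourth, the percentages say nothing about this trial. Every shift is assumed, the 56% needs a consistent half-SD preference in one direction, and arbitrary choice without a tendency gives no systematic shift. The repigmentation grade is also ordinal with six levels (0 to 5), whereas the calculations assume continuous differences without ties. All of this is true, and the figures show sensitivity only.

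Fifth, not every outcome supports six contrasts, because peri-punch repigmentation exists only in punch-treated lesions. This is also true, but the remaining outcomes are still affected.

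**Conclusion.** The concern holds and should be resolved before any lesion is treated. The protocol leaves assignment of the four lesions to unstated choice, and no other provision in it balances lesions across conditions. The conclusion that every between-lesion comparison is exposed to selection bias rests on the text alone.

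The size is conditional. With 20 pairs and a two-sided 5% paired t-test, shifts of 0.1 to 0.5 SD would give false-positive rates of 7% to 56%, or reduce 80% power to between 66% and 10%. Whether any such shift would arise, and in which direction, cannot be read from the documents.

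**What to change.** Add one rule to METHODS, ahead of LINE 1, covering all four lesions:

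1. At baseline, identify and number four lesions per patient, each suitable for any of the four conditions.
2. Record site and size and photograph each lesion.
3. Assign the numbered lesions to punch, needling, combination and control by a pre-generated random permutation, revealed only after numbering is complete.

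Then align the wording in LINE 2, LINE 3 and the control paragraph with this rule, so that no lesion is described as selected or chosen for a condition.

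**Cost.** One paragraph of amendment and a list of 20 permutations, with no extra visits. The operator loses free choice of lesion. Some patients may not have four lesions suitable for every condition, which narrows eligibility beyond the current criteria and could slow recruitment. The documents give no lesion counts, so this cannot be quantified.

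If randomisation is not adopted, the protocol should at least state that assignment is non-randomised, give the rule and who applies it, tabulate baseline site, size and depigmented area by condition, and limit causal conclusions. That costs only wording but leaves the bias in place, so it is not an equivalent remedy.

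### The blinded repigmentation grade cannot record worsening, and the surgical side-effect list has no entry for new depigmentation at treated margins or the donor site

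*Protocol*

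**What the plan says.** **Efficacy grade.** In the assessment list after LINE 3 of METHODS, two dermatologists grade repigmentation under blinding, "using a 5-point scale; grade 0 (no repigmentation), grade 1" and so on up to grade 5 for 76%-100%. There is no category below 0.

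**Other measures that could show a larger lesion.** The same list plans "Digital assessment of the size of the lesion and of the depigmented versus repigmented area using Adobe photoshop software". It also plans VASI at baseline, 3 and 6 months, "determined by the product of the area of vitiligo in hand units" and the residual depigmentation, scored by body region and summed over the body. Clinical examination, Wood's light and photography are planned at every follow-up visit. No outcome is named as primary.

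**Tolerability.** The AIM OF THE WORK names tolerability next to effectiveness. The last item of METHODS lists side effects of NB-UVB, of systemic steroids, "or of surgery (ecchymosis , scaring , cobble stoning or color mismatching) will be reported".

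**Trauma and the disease.** One of the stability criteria for entry is "Absence of history of koebner phenomenon". In LINE 2 the needle is used "going from the pigmented margins of the lesion into the vitiliginous patch", and "The procedure will be repeated for selected lesions weekly for a duration of 3 months". LINE 3 adds weekly needling of the lesion margins and of the grafted areas. LINE 1 takes closely spaced punches from a donor area, mostly gluteal.

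**The concern.** The protocol screens out patients whose skin has reacted to injury with depigmentation. It then injures pigmented skin on purpose, repeatedly at the lesion margin and once at the donor site. A screening criterion lowers a risk but does not measure it. One would therefore expect the study to record whether pigment was lost where the skin was injured.

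The two places where a reader would look for this do not hold it. The blinded grade has a floor at no repigmentation, and the surgical side-effect list has no matching item. If the scale and the list are followed as written, a lesion that lost ground at its margin is graded as showing no repigmentation, and the loss is not a listed adverse effect of the line that was used. Donor-site depigmentation is harder to recover, because no outcome is stated for that skin and the baseline photographs are described as being of the lesions.

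**Working it through.** No sample-size, power or significance figure bears on this point, so there is no plan figure to reproduce. The check goes through each planned outcome and asks whether it can register a lesion that enlarges, or pigment lost at the donor site.

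| Planned item (METHODS) | Can it show an enlarged lesion? | Can it show donor-site depigmentation? |
|---|---|---|
| Blinded grade 0-5 | No; floor at 0 | No |
| Photoshop lesion size and depigmented area | Yes, per lesion; no time points, baseline denominator, definition of worsening or blinding stated | Not stated; described for the lesion |
| VASI | Yes, by region and whole body; may not separate study lesions in the same region | In principle, through body region; not tied to the donor site |
| Peri-punch spread in mm | No; records gain only | No |
| Time to repigmentation | No; records gain only | No |
| Patient satisfaction (0-10) | Only indirectly | Only indirectly |
| Surgical side-effect list (4 items) | No item | No depigmentation item |

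**Worsening with no gain (assumed figures).** Take a fully depigmented lesion of 1.0 hand unit that grows by a fraction g.

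- Blinded grade: 0 for every g, the same as for an unchanged lesion.
- Photoshop size change: +100g%.
- VASI contribution: (1.0 + g) × 100% residual depigmentation.

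| g | Grade | Photoshop change | VASI contribution |
|---|---|---|---|
| 0% | 0 | 0% | 1.00 |
| 10% | 0 | +10% | 1.10 |
| 20% | 0 | +20% | 1.20 |
| 50% | 0 | +50% | 1.50 |

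Across the 20 lesions of one line, suppose k enlarge and 20 − k are unchanged. All 20 are grade 0 for any k from 0 to 20. The grade carries no information on k, whereas the Photoshop size would show it.

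**Gain and loss in the same lesion (assumed figures).** Set baseline area at 1.00. If 0.30 regains pigment inside the old border and 0.20 is newly lost outside it, the depigmented area is 1.00 − 0.30 + 0.20 = 0.90, a net gain of 10%. Read inside the old border, the lesion is 30% repigmented, which is grade 3 (26%-50%). Read as net change it is 10%, which is grade 2 (6%-25%). The protocol does not say which reading applies. Marginal loss can therefore be hidden in a lesion graded above 0 as well.

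**The case against.** The strongest reply is that enlargement is already measured. The Photoshop assessment is specific to the lesion, continuous and free to increase. Since no outcome is primary, it ranks equally with the grade, and a separate outcome need not feed into another. VASI can rise too, and could point to a line when the study lesions lie in different regions. This stands. A reader might infer that a growing lesion counts nowhere against efficacy, and the protocol does not support that.

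A reader might also infer that the floor inflates the mean gain by some factor. That does not follow either. Only the ordinal grade is floored, the protocol does not derive a mean percent change from it, and nothing floors the Photoshop change.

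A third inference is that the scale favours the surgical lines. The floor applies equally to the control lesion, so this holds only if treated lesions worsen more often than control lesions, and the protocol gives no rate for either. Patients are selected for six months' stability and all lesions receive background therapy, which may keep the rate low.

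On safety, the protocol does not say that unlisted events will be ignored, and loss of graft pigment may partly fall under colour mismatch. These points soften the gap but do not close it. The list is specific, and nothing in it prompts anyone to look for depigmentation at the margin or the donor site. Nor can this be left wholly to an analysis plan: the scale categories and side-effect items decide what is collected, and an unrecorded donor-site event cannot be recovered later.

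**Conclusion.** The point holds in a limited form. The blinded grade cannot distinguish an enlarged lesion from an unchanged one, and new depigmentation at the needled or grafted margin or at the donor site is not a listed tolerability event. Photoshop size and VASI would show lesion enlargement, but neither is linked to a definition of worsening or to side-effect reporting, and no outcome names the donor site.

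The text settles that the grade loses this information. The practical consequence depends on how often lesions enlarge, which the protocol does not give, so no effect on the comparison of lines is claimed. If treated lesions worsen more often than controls, the grade alone would flatter the surgical lines; if not, it would not. This is an inexpensive improvement worth making. It does not invalidate the efficacy assessment.

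**What to change.** 1. Add one category below grade 0 to the blinded reading: *depigmented area larger than at baseline*. It can be collapsed into grade 0 when results are set against the cited scale.
2. Report the Photoshop change in depigmented area as a signed percentage of the baseline area, with the number of enlarged lesions for each line and for the control.
3. Add three items to the surgical side effects recorded: new depigmentation at or beyond the treated margin, loss of graft pigment, and donor-site depigmentation.

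The cost is small. The lesion items use photographs and examinations already planned; the donor site needs a look at follow-up and, preferably, a baseline photograph. The case form gains one category and three items. The scale departs slightly from the cited one, and the results may look less favourable. No procedure, dose or treatment rule changes.
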